4.2. SUBJECT SELECTION

4.2.1. Inclusion Criteria

Subjects MUST MEET ALL of the following criteria prior to enrollment:

- Male or female ≥ 18 years of age
- Written consent must be obtained from the subject and/or their legally-authorized representative.
- Subject has a qualified chronic foot or ankle wound, sized 1 cm^2 to 25 cm^2 , for ≥ 4 weeks in duration.
- Must have necrotic tissue at least 20% of wound area
- The wound type matches one of the indicated wounds listed on the product labeling:
 - Leg ulcers
 - Pressure ulcers
 - Diabetic foot ulcers
 - First and second degree burns
 - Surgical wounds
 - Trauma wounds
- Subject has adequate circulation as demonstrated by biphasic or triphasic Doppler waveform, consistent with adequate blood flow, within 3 months prior to study enrollment. If monophasic on exam, then non-invasive tests must display Ankle Brachial Index over 0.8 and no worse than mild disease on segmental pressures.
- Subject is likely to be compliant with instructions for care, such as following institutional standard of care directions, offloading, and keeping the wound area protected from environmental contaminants
- Type I/II diabetic subjects that meet the following criteria:
 - Random blood glucose is less than 450 mg/dL within 30 days of the screening visit

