5.3.1. Wound Evaluation

Wound evaluation for data collection purposes will begin at the initial visit and thereafter during each visit at the outpatient centers where this study is going to be conducted. Wound Evaluation will include the following parameters (please also see sample Case Report Form (CRF) in Appendix D which will be used at each visit):

- Wound size (length, width and depth)
- Evaluation of Odor. Investigator assessment of wound odor will be captured via a 4-point categorical scale after each application.
- Percent of Necrotic Tissue. The percent of necrotic tissue will be assessed based on photos taken of the wound with eKare inSight® and visual confirmation from the Investigator to determine the percent covered with the necrotic tissue versus the total area of the wound. This will be entered in question six of the Bates-Jensen Wound Assessment Tool, as described in Appendix C.
- Pain Assessments. Pain will be assessed by the subject after the application (or re-application, for interim visits) of the dressing. Pain will be based on a 10-point Pain Score.
- Site Infections. Any infections at the wound site will be documented. In the event a participant develops an infection his/her participation in the study will discontinue, and the physician will implement appropriate treatment measurements.
- Bates-Jensen Wound Assessment Tool (BWAT). The BWAT will be administered to further characterize the wound. Please see Appendix C for BWAT.

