8.3. ANALYSIS OF EFFICACY DATA

8.3.1. Primary Endpoint

Percent reduction in necrotic tissue will serve as the primary endpoint. The Investigator will analyze wound photographs and visually inspect the wound in order to calculate percent necrotic tissue and enter a value of 1-5, corresponding to:

- 1 = No necrotic tissue
- 2 = 0% - 25%
- 3 = 26% - 50%
- 4 = 51% - 75%
- 5 = 76% - 100%

The 95% confidence interval for the mean reduction in necrotic tissue across the study period will be evaluated to determine if the lower bound is positive, which would be an indication of significant reduction in necrotic tissue.

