8.3.2. Secondary Endpoints

- Percent patients with 100% wound closure in each group
- Number of new infections in wound site
- Change in wound volume over time, measured similarly to percent necrotic tissue; analyzed by providing the 95% confidence interval for the mean
- Mean odor score between groups; analyzed by providing the 95% confidence interval for the mean
- Mean pain score between groups; analyzed by providing the 95% confidence interval for the mean
- Mean BWAT score between groups; analyzed by providing the 95% confidence interval for the mea

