8.3.3. Evaluable Dataset

An evaluable dataset will be used to conduct the efficacy assessments. This dataset will be defined as subjects who have at least a valid measurement for necrotic tissue from the Day 1 visit and their Final Visit, given that this will make up the measurement of the primary endpoint.

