10.3 APPENDIX C: Bates-Jenson Wound Assessment Scale

BATES-JENSEN WOUND ASSESSMENT TOOL

Instructions for use

General Guidelines:

Fill out the attached rating sheet to assess a wound's status after reading the definitions and methods of assessment described below. Evaluate once a week and whenever a change occurs in the wound. Rate according to each item by picking the response that best describes the wound and entering that score in the item score column for the appropriate date. When you have rated the wound on all items, determine the total score by adding together the 13-item scores. The HIGHER the total score, the more severe the wound status is. Plot total score on the Wound Status Continuum to determine progress. If the wound has healed/resolved, score items 1, 2, 3 and 4 as =0.

Specific Instructions:

1. **Size:** Use ruler to measure the longest and widest aspect of the wound surface in centimeters; multiply length x width. Score as = 0 if wound healed/resolved.
2. **Depth:** Pick the depth, thickness, most appropriate to the wound using these additional descriptions, score as
0 = if wound healed/resolved:
1 = tissues damaged but no break in skin surface.
2 = superficial, abrasion, blister or shallow crater. Even with, &/or elevated above skin surface (e.g., hyperplasia).
3 = deep crater with or without undermining of adjacent tissue. 4 = visualization of tissue layers not possible due to necrosis. 5 = supporting structures include tendon, joint capsule.
3. **Edges:** Score as = 0 if wound healed/resolved. Use this guide:

Indistinct, diffuse	=	unable to clearly distinguish wound outline.
Attached	=	even or flush with wound base, no sides or walls present; flat.
Not attached	=	sides or walls are present; floor or base of wound is deeper than edge.
Rolled under, thickened	=	soft to firm and flexible to touch.
Hyperkeratosis	=	callous-like tissue formation around wound & at edges.
Fibrotic, scarred	=	hard, rigid to touch.

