Circle and date appropriate description:

Irregular

Linear or elongated

Round/oval

Bowl/boat

[figure not shown]
Square/rectangle

Butterfly

Other Shape

Item	Asses	Date Score	Date Score	Date Score
1. Size*	*0 = Healed, resolved wound 1 = Length x width <4 sq cm 2 = Length x width 4--≤16 sq cm 3 = Length x width 16.1--≤36 sq cm 4 = Length x width 36.1--≤80 sq cm 5 = Length x width >80 sq cm			
2. Depth*	*0 = Healed, resolved wound 1 = Non-blanchable erythema on intact skin 2 = Partial thickness skin loss involving epidermis &/or dermis 3 = Full thickness skin loss involving damage or necrosis of subcutaneous tissue; may extend down to but not through underlying fascia; &/or mixed partial & full thickness &/or tissue layers obscured by granulation tissue 4 = Obscured by necrosis 5 = Full thickness skin loss with extensive destruction, tissue necrosis or damage to muscle, bone or supporting structures			
3. Edges*	*0 = Healed, resolved wound 1 = Indistinct, diffuse, none clearly visible 2 = Distinct, outline clearly visible, attached, even with wound base 3 = Well-defined, not attached to wound base 4 = Well-defined, not attached to base, rolled under, thickened 5 = Well-defined, fibrotic, scarred or hyperkeratotic			
4. Under-mining*	*0 = Healed, resolved wound 1 = None present 2 = Undermining < 2 cm in any area 3 = Undermining 2-4 cm involving < 50% wound margins 4 = Undermining 2-4 cm involving > 50% wound margins 5 = Undermining > 4 cm or Tunneling in any area			
5. Necrotic Tissue Type	1 = None visible 2 = White/grey non-viable tissue &/or non-adherent yellow slough 3 = Loosely adherent yellow slough 4 = Adherent, soft, black eschar 5 = Firmly adherent, hard, black eschar			

6. Necrotic Tissue Amount	1 = None visible 2 = < 25% of wound bed covered 3 = 25% to 50% of wound covered 4 = > 50% and < 75% of wound covered 5 = 75% to 100% of wound covered		
7. Exudate Type	1 = None 2 = Bloody 3 = Serosanguineous: thin, water, pale red/pink 4 = Serous: thick, watery, clear 5 = Purulent: thin or thick, opaque, tan/yellow, with or without odor		
8. Exudate Amount	1 = None, dry wound 2 = Scant, wound moist but no observable exudate 3 = Small 4 = Moderate 5 = Large		
9. Skin Color Surrounding Wound	1 = Pink or normal for ethnic group 2 = Bright red &/or blanches to touch 3 = White or grey pallor or hypopigmented 4 = Dark red or purple &/or non-blanchable 5 = Black or hyperpigmented		

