10.4 APPENDIX D: Case Report Form

Case Report Form (R16-017)

Subject Number:	Visit Date:	Visit Time:	AM	PM	Visit Type and Number:	
Height (inches):	Weight (lbs):	Age:				
Sex:  Male	 Female					
Race:  White	 Black	 Hispanic or Latino	 Asian	 Other/Mixed Race	 Native American	
Was mechanical debridement used?  Yes		 No				
Was a secondary dressing used?  Yes		 No	If yes, what kind? _____			
Wound Assessment						
Physical Examination and Wound Zoom Analysis			Bates – Jensen Wound Assessment Tool (BWAT)			

Diagnosis: _____
 
What is the percent of necrotic tissue? _____ %
 
Wound size (cm): Width _____ x Length _____ x Depth _____
 
Evaluation of odor: _____
 
 1  2  3  4
 
VAS Pain scale score within 10 minutes following dressing change: _____
 
 0  1  2  3  4  5  6  7  8  9  10
 
Site Infection: Yes No
 
If yes, discontinue subject and note steps taken:
			
1. Skin: _____
 
2. Depth: _____
 
3. Edges: _____
 
4. Undermining: _____
 
5. Necrotic Tissue Type: _____
 
6. Necrotic Tissue Amount: _____
 
7. Exudate Type: _____
 
8. Exudate Amount: _____
 
9. Skin Color Surrounding Wound: _____
 
10. Peripheral Tissue Edema: _____
 
11. Peripheral Tissue Induration: _____
 
12. Granulation Tissue: _____
 
13. Epithelialization: _____
 
TOTAL BWAT SCORE: _____
			

Place photograph of the wound from the Wound Zoom camera below:

Subject #: _____ **Date:** _____

*Please note that the information in the picture should match the above information.

Signature _____ **Date** _____

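### Change in wound volume rests on a Day 1 depth that necrosis can obscure, so successful debridement can make true shrinkage look smaller than it is

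*Combined protocol and SAP*

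**What the plan says.** Section 8.3.2 defines the endpoint in one line: "Change in wound volume over time, measured similarly to percent necrotic tissue; analyzed by providing the 95% confidence interval for the mean". It gives no formula for volume, no rule for a depth that cannot be seen, and no success criterion.

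The other pieces are spread across the protocol:

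- Entry (section 4.2.1): "Must have necrotic tissue at least 20% of wound area". This is a minimum; there is no upper limit.
- Measurement (section 5.3.1 and the case report form in Appendix D): length, width and depth are recorded from the initial visit onward. The form's field reads "Wound size (cm): Width _____ x Length _____ x Depth" and has no option for a depth that is not measurable.
- Depth scale (Appendix C, Bates-Jensen item 2): the instructions define "4 = visualization of tissue layers not possible due to necrosis", and the rating sheet has "4 = Obscured by necrosis".
- Primary endpoint (section 8.3.1): "Percent reduction in necrotic tissue will serve as the primary endpoint".
- Evaluable set (section 8.3.3): "subjects who have at least a valid measurement for necrotic tissue from the Day 1 visit and their Final Visit". Validity is required for necrosis, not for depth or volume.
- Debridement (section 5.3.4): mechanical debridement is allowed as standard care and noted. Its timing relative to the depth measurement is not stated.

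**The concern.** The primary and volume endpoints share a baseline condition that acts on them in opposite directions. Necrosis on Day 1 is what the dressing is meant to remove. It is also what can prevent the base of the wound from being seen. If depth is taken to the surface of slough or eschar, the Day 1 volume is too small. Once the base is exposed, depth rises for a reason unrelated to worsening.

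This error is systematic and tied to treatment success. It is largest where the most covering tissue is cleared, and with no comparison group nothing cancels it. The study could report less necrosis together with little or no fall in volume, with part of the contrast produced by measurement alone. No section says how an obscured Day 1 depth is taken, whether it is treated as missing, or how a rise in volume after debridement should be read.

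**Working it through.** The plan gives no volume, depth or standard deviation, so there is no figure to reproduce. Section 8.2 sets 20 evaluable subjects and a t-based 95% interval for necrotic tissue reduction. Applying the same method to volume, t(0.975, 19 df) = 2.093 and the half-width is 2.093/√20 = 0.468 SD.

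**Assumptions.** Volume is taken as length × width × depth. Let s be the true fractional fall in volume, h the share of true Day 1 volume hidden under necrosis, and f the share of subjects with hidden depth. The final depth is assumed to be read correctly. All values of s, h and f below are assumed.

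**One wound.** Recorded Day 1 volume is (1 − h) of the true value and final volume is (1 − s) of it, so

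recorded change = (1 − s)/(1 − h) − 1.

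The sign reverses when h > s. With s = 0.30:

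| h | Recorded volume change |
|---|---|
| 0 | −30% |
| 0.2 | −13% |
| 0.3 | 0% |
| 0.4 | +17% |
| 0.6 | +75% |

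In dimensions: Day 1 recorded as 3.0 × 2.0 × 0.3 cm = 1.80 cm³; final 2.7 × 1.8 × 0.5 cm = 2.43 cm³. Area goes from 6.00 to 4.86 cm² (−19%), while recorded volume rises by 2.43/1.80 − 1 = 35%. If the true Day 1 depth was 0.5 cm, true Day 1 volume was 3.00 cm³, so h = 1 − 1.80/3.00 = 0.40, s = 1 − 2.43/3.00 = 0.19, and 0.81/0.60 − 1 = +35%, as the formula gives.

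Equivalently, an area reduction a is cancelled once recorded depth rises by a factor of 1/(1 − a): 1.25 for 20%, 1.45 for 31% and 2.0 for 50%.

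**Cohort mean.** In units of true Day 1 volume, and with the same s in subjects with and without hidden depth, the mean apparent reduction is s − f·h. The last two columns come from 20,000 simulated trials per row with n = 20, mean s = 0.30 and an assumed between-subject SD of 0.40 (half-width about 0.468 × 40 = 19 points):

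| f | h | Mean apparent reduction | 95% CI shows reduction | 95% CI shows growth |
|---|---|---|---|---|
| 0 | 0 | 30% | 89% | 0% |
| 0.25 | 0.4 | 20% | 49% | <0.1% |
| 0.5 | 0.4 | 10% | 15% | 0.1% |
| 0.5 | 0.6 | 0% | about 3% | about 3% |
| 1 | 0.4 | −10% | 0.1% | 18% |

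When only some subjects have hidden depth, the main effect in these scenarios is to attenuate a real reduction. Mean apparent growth needs f·h > s.

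**The case against.** The strongest reply is that the key step is an inference. Bates-Jensen item 2 is an ordinal rating of which tissue layers can be seen. It does not say that depth in centimetres is read to the top of dead tissue, and no section describes how that depth is taken. Nor does section 8.3.2 state that volume is the product of three dimensions. This stands: the mechanism is documented as possible, not as the trial's method. The undefined volume measurement is itself part of the problem, and the comparison with percent necrosis does not settle it, because percent necrosis is a share of area coded 1 to 5.

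Several stronger readings are tempting but unsupported:

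- A reader might infer that necrosis hides depth in every subject. The 20% minimum is a share of area, so much of the bed may be visible, and obscured depth is only one level of item 2.
- A reader might infer that the cohort result will show worsening. That depends on s, f and h, none of which the documents give.
- A reader might infer that a good responder would be classed as a failure on volume. No responder or failure rule exists for volume; the positive-lower-bound criterion in section 8.3.1 applies to necrotic tissue only.
- A reader might infer that percent change becomes unstable near a zero baseline. Section 8.3.2 specifies change, not percent change.
- A reader might infer that volume is the only graded measure of healing. The Bates-Jensen total is also analysed as a mean and includes size, granulation and epithelialization.

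It is also fair to say that this is one secondary endpoint in a small uncontrolled study, and that the data needed to identify obscured baselines are already collected. That limits the consequence and makes the remedy cheap.

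**Conclusion.** The concern holds as a weakness in one secondary endpoint. In a population selected for necrosis, the mean volume change can understate true shrinkage, and an individual wound can be recorded as larger although it has shrunk, whenever the hidden share of its Day 1 volume exceeds its true fractional shrinkage. The plan has no rule for this.

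The size rests on assumed values. With a true 30% fall, hiding 40% of Day 1 volume in a quarter of subjects lowers the apparent mean reduction to 20%; in half of them, to 10%. The proportion affected and the net cohort effect cannot be derived from the documents. The conclusion also assumes that depth in centimetres is under-read in at least some necrotic wounds and that volume is built from that depth. The primary analysis is not affected.

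**What to change.** In section 8.3.2:

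1. Add change in wound area from Day 1 to Final Visit, with its 95% CI, as the wound-size endpoint on which the interpretation of healing rests. Use either the eKare area or length × width from the case report form, and name which one.
2. Keep volume change from Day 1 as a supporting description, and state its formula.
3. Report the number of subjects whose Day 1 Bates-Jensen item 2 score is 4.
4. Add a volume sensitivity analysis restricted to subjects whose Day 1 depth was not obscured. Do not move the baseline to the first visit with a visible base: that would be a post-treatment baseline, would shorten follow-up unequally, and would leave no change to compute if the base first appears at the Final Visit.

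The cost is a wording change. Length, width and item 2 are already recorded at each wound evaluation; the sample form has no area field, so eKare area would have to be taken from the camera. There are downsides. Area does not capture the filling-in of deep wounds, and a score of 4 will not flag every slough-filled wound. The documents also do not say whether debridement alters recorded length and width. Volume is therefore retained and read with these caveats.

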3.2. SECONDARY OBJECTIVES

To evaluate the efficacy of TheraHoney® Foam Flex in the promotion of granulation and re-epithelialization in chronic wounds.

To evaluate the safety and ease of use of TheraHoney® Foam Flex when applied to chronic wounds.

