4. **Undermining:** Score as = 0 if wound healed/resolved. Assess by inserting a cotton tipped applicator under the wound edge; advance it as far as it will go without using undue force; raise the tip of the applicator so it may be seen or felt on the surface of the skin; mark the surface with a pen; measure the distance from the mark on the skin to the edge of the wound. Continue process around the wound. Then use a transparent metric measuring guide with concentric circles divided into 4 (25%) pie-shaped quadrants to help determine percent of wound involved.
5. **Necrotic Tissue Type:** Pick the type of necrotic tissue that is predominant in the wound according to color, consistency and adherence using this guide:

White/gray non-viable tissue	=	may appear prior to wound opening; skin surface is white or gray.
Non-adherent, yellow slough	=	thin, mucinous substance; scattered throughout wound bed; easily separated from wound tissue.
Loosely adherent, yellow slough	=	thick, stringy, clumps of debris; attached to wound tissue.
Adherent, soft, black eschar	=	soggy tissue; strongly attached to tissue in center or base of wound.
Firmly adherent, hard/black eschar	=	firm, crusty tissue; strongly attached to wound base and edges (like a hard scab).

© 2001 Barbara Bates-Jensen

6. **Necrotic Tissue Amount:** Use a transparent metric measuring guide with concentric circles divided into 4 (25%) pie-shaped quadrants to help determine percent of wound involved.

7. **Exudate Type:** Some dressings interact with wound drainage to produce a gel or trap liquid. Before assessing exudate type, gently cleanse wound with normal saline or water. Pick the exudate type that is predominant in the wound according to color and consistency, using this guide:

Bloody	=	thin, bright red
Serosanguineous	=	thin, watery pale red to pink
Serous	=	thin, watery, clear
Purulent	=	thin or thick, opaque tan to yellow or green may have offensive odor

8. **Exudate Amount:** Use a transparent metric measuring guide with concentric circles divided into 4 (25%) pie- shaped quadrants to determine percent of dressing involved with exudate. Use this guide:

None	=	wound tissues dry.
Scant	=	wound tissues moist; no measurable exudate.
Small	=	wound tissues wet; moisture evenly distributed in wound; drainage involves $\leq 25\%$ dressing.
Moderate	=	wound tissues saturated; drainage may or may not be evenly distributed in wound; drainage involves $> 25\%$ to $\leq 75\%$ dressing.

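### The BWAT total contains the primary necrosis reading (item 6) and a second necrosis item (item 5), so a fall in it is not independent evidence of granulation or re-epithelialization

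*Combined protocol and SAP*

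**What the plan says.** - **Primary endpoint.** Section 8.3.1 has the Investigator judge the percentage of necrotic tissue and "enter a value of 1-5, corresponding to" five bands, from none to 76–100%. Section 5.3.1 says of the same assessment: "This will be entered in question six of the Bates-Jensen Wound Assessment Tool, as described in Appendix C".
- **BWAT total.** Appendix C tells the rater to "determine the total score by adding together the 13-item scores", and adds: "The HIGHER the total score, the more severe the wound status is". The case report form (Appendix D) lists the 13 items and one total, with no sub-score.
- **Item 5.** Appendix C instructs: "Pick the type of necrotic tissue that is predominant in the wound". The score is 1 when none is visible and otherwise 2 to 5.
- **Secondary endpoint.** Section 8.3.2 lists "Mean BWAT score between groups; analyzed by providing the 95% confidence interval". It excludes no item and defines no sub-score.
- **Secondary objective.** Section 3.2 reads "To evaluate the efficacy of TheraHoney® Foam Flex in the promotion of granulation and re-epithelialization in chronic wounds". In the BWAT these two attributes are items 12 and 13. No other endpoint in Section 8.3.2 contains them as such.
- **Entry.** Section 4.2.1 requires necrosis over at least 20% of the wound area.

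**The concern.** The primary result is counted again inside a secondary endpoint. Item 6 is filled from the same assessment as the primary, and item 5 also returns to its minimum when necrosis clears. The entry rule means that both items start above their minimum in every subject and have room to fall.

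This matters because of the secondary objective. BWAT is the only listed endpoint that holds granulation and epithelialization items, so a reader looking for an answer on that objective will turn to it. A lower total could mean that the wound is granulating and resurfacing, or only that necrosis fell, which the primary already reports. The plan gives no means of telling these apart and does not mention the overlap.

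**Working it through.** There is no figure of the plan's own to reproduce: Section 8.2 sets 20 evaluable subjects and gives no SD, effect or interval width.

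**1. Share of the score (from the documents).** For an open wound with all 13 items scored 1 to 5, the total runs from 13 to 65, a span of 52.
- Item 6 alone: 5 − 1 = 4 points; 4/52 = 7.7%.
- Items 5 and 6: 8 points; 8/52 = 15.4%.

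**2. Smallest effect of full debridement.** At 20% necrosis or more, item 6 is at least 2 and item 5 is at least 2. Full clearance takes both to 1. With the other 11 items unchanged, the total falls by at least (2 − 1) + (2 − 1) = 2 points, of which at least 1 is item 6.

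**3. When a fall of that size excludes 0.** For a one-sample 95% t interval with n = 20, t(0.975, 19) = 2.093, and the half-width is 2.093/√20 × SD = 0.468 × SD. An observed mean fall d excludes 0 when the SD of change is below d/0.468:
- d = 1: SD below 2.14
- d = 2: SD below 4.27
- d = 4: SD below 8.55

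**4. How often necrosis alone would do it (all inputs assumed).** The other items have zero mean change, and s is the SD of their summed change, taken as uncorrelated with the necrosis items. The probability that the lower bound exceeds 0 is P(T > 2.093), where T is noncentral t with 19 df and noncentrality mean × √20 / SD.

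- *Case A:* items 5 and 6 fall by 1.2 and 1.5 (mean 2.7), SD 1 each, correlation 0.5. SD of total = √(1 + 1 + 2 × 0.5 + s²) = √(3 + s²).
- *Case B:* only item 6 falls, by 1.5, SD 1; item 5 does not change. SD of total = √(1 + s²).

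| s | Case A: SD of total | Case A: probability | Case B: SD of total | Case B: probability |
|---|---|---|---|---|
| 2 | 2.65 | 0.99 | 2.24 | 0.81 |
| 3 | 3.46 | 0.91 | 3.16 | 0.52 |
| 4 | 4.36 | 0.75 | 4.12 | 0.34 |
| 5 | 5.29 | 0.58 | 5.10 | 0.24 |
| 6 | 6.24 | 0.45 | 6.08 | 0.18 |
| 8 | 8.19 | 0.29 | 8.06 | 0.12 |

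The range of s is carried to 8 because eleven items with SD 1 each have a summed SD of √11 = 3.3 if uncorrelated, and √(11 + 11 × 10 × 0.5) = √66 = 8.1 at the correlation of 0.5 used for items 5 and 6.

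**5. With items 5 and 6 removed.** If the remaining 11 items have zero mean change, the probability returns to about 0.025 whatever the SD (simulated 0.024 to 0.028).

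**The case against.** The strongest reply is that Section 8.3.2 sets no test for BWAT. The positive-lower-bound rule is stated only for the primary. The BWAT entry asks for a mean score with an interval, without a change from Day 1 or a success threshold, and its reference to groups does not fit a one-group study. An interval for a mean raw score always lies above 0, since even a healed wound scores at least 9 (items 1 to 4 at 0, nine items at 1). This stands: the calculation applies only once the endpoint is defined as a change, and that definition is itself missing. Reading the endpoint as the total is also an inference, from Appendices C and D.

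Second, BWAT is a standard wound-status score, necrosis belongs in it, and any composite overlaps with its parts. Closure and wound volume are listed as separate healing endpoints. This stands as a reason to keep the total. It does not answer the objective in Section 3.2, because neither of those endpoints measures granulation, and closure captures epithelialization only when it is complete.

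Two stronger readings are tempting:
- **That the total would probably improve from the primary alone.** A reader might infer this from the top rows of Case A. The documents do not support it: the primary is item 6 only, item 5 rates a different attribute (type and adherence), and the probabilities rest on SDs that the documents do not give.
- **That the plan presents BWAT as confirmation of healing.** It does not. Section 5.3.1 uses BWAT to describe the wound further, and misreading is a risk, not something the plan asserts.

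**Conclusion.** The overlap is real and follows from the documents: up to 4 of 52 points from the primary reading itself, up to 8 of 52 with item 5, and a fall of at least 2 points on full debridement if nothing else changes. A fall in the 13-item total is therefore not independent evidence of granulation or re-epithelialization.

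How often this alone would produce an interval excluding 0 is uncertain: 0.99 to 0.29 in Case A and 0.81 to 0.12 in Case B, for s from 2 to 8. These figures assume that the endpoint is analysed as change from Day 1 and that the other items have no mean change and vary independently of the necrosis items.

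Severity is minor. This is one of six secondary endpoints in an uncontrolled study of 20 subjects, and the primary analysis is untouched. It is worth correcting because the granulation and re-epithelialization objective otherwise has no clear measure.

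**What to change.** In Section 8.3.2:
1. Replace the BWAT entry with the mean change in BWAT from Day 1 to Final Visit, and drop the reference to groups.
2. Keep the standard 13-item total, with its 95% interval.
3. Add, each with a 95% interval, the change in the total without items 5 and 6 (11 items, supportive) and the changes in item 12 (granulation) and item 13 (epithelialization).
4. State that the 13-item total is not independent of the primary endpoint, and that the granulation and re-epithelialization objective is judged on items 12 and 13.

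Cost: a few extra table rows and no new data, since Appendix D already records every item. The 11-item sum is a non-standard score, still mixes in attributes such as exudate and edema, and is not wholly free of necrosis, because item 2 has a level for depth hidden by necrotic tissue. It should therefore support the total and not replace it.
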